3. STUDY POPULATION

3.1 List the number of subjects to be enrolled

We will recruit 74 patients in total, and with a dropout rate of 15%, we will have a sample size of 64. With 64 patients, 32 in each group, we can detect a large effect size with 1 degree of freedom, alpha of 0.05 at 80% power.

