3.3 Inclusion Criteria

Sixty-four subjects will be recruited amongst patients attending the Clinic for Graduate Periodontics, Graduate Prosthodontics, or the UTDentists, who have at least one implant with peri-implant inflammation that requires non-surgical treatment. Peri-implant diseases included are peri-implant mucositis and peri-implantitis. All subjects will be ≥ 18 -year-old and systemically healthy or with controlled common systemic conditions, such as hypertension, that will not affect wound healing. Criteria for diagnosis of peri-implant mucositis or peri-implantitis:

1. Red, swollen gingival tissues surrounding the implant
2. Presence of bleeding and/or suppuration on gentle probing around the implant
3. Increased probing depth compared to probing depth after restoration of the implant (greater than 2mm increase in probing depth)
4. May or may not have progressive bone loss in relation to radiographic bone levels assessed either 1 year following restoration of the implant OR ≥ 3 mm of radiographic bone loss from the implant platform

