3.6 Subject Replacement

Subjects who withdraw from the study can be replaced. However, to complete the study within the time allocated, the center will not enroll subjects after 24 months from enrollment initiation.

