5. STUDY DESIGN

5.1 Summary of Study Design

This is randomized double blinded clinical control study designed to assess improved clinical and microbiological outcomes with the use of laser antimicrobial photodynamic therapy (aPDT) as an adjunct to the gold standard of mechanical debridement in the treatment of peri-implant diseases. Seventy-four patients will be recruited. Clinical measurements including bleeding on probing, pocket depth, plaque, and clinical attachment will be measured at baseline, 6 weeks, and 12 weeks after therapy. The 2017 World Shop classification will be used to diagnosis implants as peri-implant mucositis or peri-implantitis (as stated above in section 3.3). Only diseased implants will be included and only one implant per patient will be studied. The hypothesis is that inflamed implant sites treated with mechanical debridement and adjunctive aPDT will have greater reduction in bleeding and pocket depth reduction than those sites treated with mechanical debridement alone. The potential for greater healing and greater antibacterial activity on the implant surface will benefit patients who have peri-implant diseases. The results can be applied in the managing and in the armamentarium for treatment of both peri-implantitis and peri-implant mucositis.

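### Minor: 74 recruited with 15% dropout leaves about 63 patients, not the stated 64, and section 3.3 gives 64 as the number recruited

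*Combined protocol and SAP*

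**What the plan says.** Section 3.1 gives the recruitment target, the dropout allowance and the number left: "We will recruit 74 patients in total, and with a dropout rate of 15%, we will have a sample size of 64". It then splits that number equally ("With 64 patients, 32 in each group") and attaches the power claim to it: "we can detect a large effect size with 1 degree of freedom", at alpha 0.05 and 80% power. Section 11.1 repeats the 74, the 15%, the 64 and the power claim, without the split by group.

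The design summary in section 5.1 agrees on recruitment: "Seventy-four patients will be recruited". Section 3.3 does not: "Sixty-four subjects will be recruited amongst patients attending the Clinic".

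Section 3.6 adds that "Subjects who withdraw from the study can be replaced", with no enrolment later than 24 months after enrolment begins. It does not say whether replacements count within the 74.

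**The concern.** The sentence in 3.1 and 11.1 is the plan's only sample-size calculation, and the power claim rests on the 64 it produces. A reader who removes 15% from 74 does not get 64. The number on which power is stated is therefore not the number that the plan's own dropout rate delivers.

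Section 3.3 adds to the confusion by using 64, elsewhere the number left after dropout, as the number recruited. If only 64 were recruited and 15% were lost, 64 × 0.85 = 54.4 would remain. At stake is a clear statement of how many patients are recruited, how many are expected to be retained, and which of the two the power refers to.

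**Working it through.** **Inputs.** Recruited 74 (3.1, 5.1, 11.1); dropout 15% (3.1, 11.1); retained 64 (3.1, 11.1), as 32 per group (3.1); alpha 0.05 and power 80% (3.1, 11.1). No numeric effect size, standard deviation, event rate, test or sidedness is given.

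**Reproducing the plan's figure.**
- Adding 15% to the number retained: 64 × (1 + 0.15) = 73.6, rounded up to 74. This gives the stated 74 and is its likely source.
- Dividing by the proportion retained: 64/(1 − 0.15) = 75.3, or 76 for equal groups.

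**What 15% dropout from 74 leaves.** 74 × (1 − 0.15) = 62.9. In whole patients:

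| Lost | Retained | Loss |
|---|---|---|
| 10 | 64 | 10/74 = 13.5% |
| 11 | 63 | 11/74 = 14.9% |
| 12 | 62 | 12/74 = 16.2% |

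The whole number closest to 15% is 63 retained. The gap from the plan is 64 − 62.9 = 1.1 patients, or 1.1/64 = 1.7%.

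**Effect on power, comparison of means.** Assume a two-sided two-sample t-test at 0.05 and take large to mean d = 0.8; both are assumptions. The noncentrality is d × √(n₁n₂/(n₁ + n₂)).
- 32 and 32: 0.8 × √16 = 3.20, power 88.3%.
- 31 and 32: 0.8 × √(992/63) = 3.17, power 87.8%.
- 31 and 31: 0.8 × √15.5 = 3.15, power 87.3%.

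The difference detectable at 80% power is d = 0.711 with 32 per group and d = 0.723 with 31 per group.

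**Effect on power, 1-df chi-square.** Suppose instead that 64 was chosen to give exactly 80% on a chi-square test with one degree of freedom. The effect is then w = 0.350, with noncentrality N × w².
- N = 64: power 80.0%.
- N = 63: power 79.4%.
- N = 62: power 78.7%.

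**Sensitivity to the meaning of large.** With 32 per group and the same t-test, power is 78.7% at d = 0.7 and 88.3% at d = 0.8. The undefined effect size moves power by about ten points; the dropout slip moves it by less than one at 63 and by about one at 62.

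**The case against.** The best defence is that this is a planning forecast, that 62.9 is within 2 patients of 64, and that nothing in the design, analysis or interpretation turns on one patient. That stands, and it is why the point is minor. It does not make the sentence correct: no rounding of a 15% loss from 74 gives 64.

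A second defence is that patients who drop out are not necessarily lost to the analysis. Section 11.2 plans mixed-effects models over weeks 0, 6 and 12 and states no restriction to completers, so a patient lost after week 6 could still contribute. This also stands. The plan's own sentence, however, takes 15% off to reach its sample size, and the check holds it to that definition.

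A reader might go further in three ways that the documents do not support.

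- **That the replacement rule contradicts a total of 74.** Section 3.6 permits replacement, does not require it, and limits it in time. Replacements could fall within the 74 or come on top of it. That is an ambiguity, not a conflict. Nor does the plan say that replacement continues until 74 have completed, so no larger randomised total can be derived from it.
- **That the trial is underpowered because of this slip.** The shift is about one point or less, and on one reasonable assumption power stays well above 80%.
- **That the 80% claim is therefore confirmed.** It is not. That result depends on an assumed test and an assumed d = 0.8. On the chi-square reading above, 63 falls just below 80%.

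**Conclusion.** A minor arithmetic error. At the stated 15% dropout, 74 recruited leaves about 63 patients, not 64; 64 retained corresponds to 13.5%. The likely cause is multiplying by 1.15 where division by 0.85 was needed. This part needs no assumption beyond the plan's own figures.

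The consequence for power is about one point or less: 88.3% to 87.8% at 63, or to 87.3% at 62, under a two-sided t-test with d = 0.8; 80.0% to 79.4% at 63 for a 1-df chi-square set to 80% at 64. Whether power is 80% at either number cannot be settled from the documents.

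The ten-patient disagreement on recruitment, 64 in section 3.3 against 74 in 3.1, 5.1 and 11.1, is a plain contradiction. The dropout sentence suggests that 64 in 3.3 is the number retained, put in the wrong place, but the plan does not say so.

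**What to change.** In 3.1 and 11.1, do one of the following:

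1. Keep 74 and 15%, and restate the expected number retained as about 63 (31 and 32 per group).
2. Keep 74 and 64, and state that 74 allows for about 13.5% dropout.

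Attach the power statement to whichever number is kept. Name the test, the sidedness and the numeric effect size behind it, so that the 80% can be checked.

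In the same edit, reconcile the recruitment number in 3.3 with the 74 in 3.1, 5.1 and 11.1. If 74 is intended, 3.3 should say so and leave the retained number to 3.1. A sentence in 3.6 saying whether replacements count within the 74 would remove the ambiguity there.

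The cost is wording in three or four sections. Neither option needs more patients. Keeping both 64 and 15% would mean recruiting 76, two more than planned; the small effect on power does not require it.

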3.2 Criteria for Recruitment

The patients who need non-surgical treatment of implants that are suffering peri-implant diseases will be recruited in the study. These patients should be systemically healthy to receive this procedure.

3.3 Inclusion Criteria

Sixty-four subjects will be recruited amongst patients attending the Clinic for Graduate Periodontics, Graduate Prosthodontics, or the UTDentists, who have at least one implant with peri-implant inflammation that requires non-surgical treatment. Peri-implant diseases included are peri-implant mucositis and peri-implantitis. All subjects will be ≥ 18 -year-old and systemically healthy or with controlled common systemic conditions, such as hypertension, that will not affect wound healing. Criteria for diagnosis of peri-implant mucositis or peri-implantitis:

1. Red, swollen gingival tissues surrounding the implant
2. Presence of bleeding and/or suppuration on gentle probing around the implant
3. Increased probing depth compared to probing depth after restoration of the implant (greater than 2mm increase in probing depth)
4. May or may not have progressive bone loss in relation to radiographic bone levels assessed either 1 year following restoration of the implant OR ≥ 3 mm of radiographic bone loss from the implant platform

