11. SAMPLE SIZE AND STATISTICAL METHODS

11.1 Determination of Sample Size

We will recruit 74 patients in total, and with a dropout rate of 15%, we will have a sample size of 64. With 64 patients, we can detect a large effect size with 1 degree of freedom at an alpha equal to 0.05 with 80% power between the two treatments.

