11.2 Statistical and Analytical Plans

a. General Consideration

We will present means and standard deviations for completeness of the report. The statistical significance level to test the primary endpoint was set at $p<0.05$.

b. Safety Analyses

Safety will be evaluated by tabulations of adverse events and will be presented with descriptive statistics at baseline and follow-up visits each month.

Adverse events will be classified as severe complications and summarized for baseline and follow-up visits.

All information pertaining to adverse events noted during the study will be listed by subject, detailing verbatim given by the investigator, preferred term, date of onset, date of resolution, severity, and relationship to procedure. The onset of adverse events will also be shown relative (in number of days) to the day of performing the surgery.

c. Statistical Analysis Plan

We will analyze these data sets using generalized linear mixed effects models with the appropriate error structure (e.g., binomial, poisson) and specifying treatment (control mechanical debridement vs mechanical debridement + aPDT) as a fixed factor and repeated measures of individuals over 0, 6, and 12 weeks as a random factor. Demographic data collected from patients will be included in analysis and will be adjusted for any confounders. All quantitative analyses will be performed in R Statistical Software (R Core Team 2017).

For microbiologic analysis, microbial DNA will be purified using the QIAmp DNA Mini Kit (Qiagen, Hilden, Germany) or Qiagen DNA MiniAmp kit (Qiagen, Valencia, CA, USA), according to the manufacturer's protocol. 16S rRNA gene V4 amplification and sequencing will be completed. 16S rRNA gene data analysis will also be completed for the plaque samples.

For immunologic analysis, the PerioPaper strips will be analyzed using multiplexed fluorescent bead-based immunoassay. Assessments will be made in triplicate, and for the statistical analysis, median of the replicates will be used.

12. Ethical Consideration

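### Section 3.3 gives 64 as the number to recruit; sections 3.1, 5.1 and 11.1 give 74, and 64 is elsewhere the number left after 15% dropout

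*Combined protocol and SAP*

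**What the plan says.** Four places in the combined protocol and SAP state how many patients will be recruited.

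- Section 3.3 (Inclusion Criteria): "Sixty-four subjects will be recruited amongst patients attending the Clinic for Graduate Periodontics, Graduate Prosthodontics, or the UTDentists".
- Section 5.1 (Summary of Study Design): "Seventy-four patients will be recruited".
- Section 11.1, where the number is justified, reads: "We will recruit 74 patients in total, and with a dropout rate of 15%, we will have a sample size of 64".
- Section 3.1 (number of subjects to be enrolled) gives the same 74, 15% and 64, and adds: "With 64 patients, 32 in each group, we can detect a large effect size with 1 degree of freedom", at an alpha of 0.05 and 80% power.

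Two other provisions bear on the consequence. Section 3.6 permits replacement of withdrawals ("Subjects who withdraw from the study can be replaced") but sets a limit: "the center will not enroll subjects after 24 months from enrollment initiation". Section 11.2 plans a generalized linear mixed model that includes "repeated measures of individuals over 0, 6, and 12 weeks as a random factor".

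**The concern.** All four sections describe recruitment into the same trial. In 3.3 the number 64 is how many patients enter. In 3.1 and 11.1 it is how many are left once dropout has been taken off. It cannot be both, and 3.3 does not say that it means anything other than recruitment.

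The power statement is tied to 64 patients, 32 per group, after dropout. If the centre took its target from the eligibility section and stopped at 64, the plan's own dropout allowance would have to come out of the 64. The trial could then be about 10 patients smaller than the one described.

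**Working it through.** **Inputs from the documents.** Recruit 74 (3.1, 5.1, 11.1) or 64 (3.3). Dropout 15% (3.1, 11.1). Sample size after dropout 64, 32 per group (3.1). Alpha 0.05, power 80%, 1 degree of freedom (3.1, 11.1). No test, sidedness or numerical effect size is given.

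**Step 1: reproduce the plan's 74.** Inflating 64 by multiplication gives 64 × 1.15 = 73.6, which rounds up to 74. This matches and supports reading 64 as the post-dropout number and 74 as the recruitment number. Inflating by division gives 64 / 0.85 = 75.3, or 76, two patients more.

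**Step 2: patients remaining after 15% dropout, none replaced.**

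- Recruit 74: 74 × 0.85 = 62.9, about 63.
- Recruit 64: 64 × 0.85 = 54.4, about 54, or 27 per arm. Withdrawals are 64 × 0.15 = 9.6, about 10.

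The gap between targets is 74 − 64 = 10. Following 3.3 also leaves 64 − 54 = 10 fewer than the number behind the power statement.

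**Step 3: what the shortfall means for power.** This needs assumptions: a two-sided two-sample t-test at 0.05, equal arms of n after dropout, and 0.8 SD as the meaning of a large effect. Power comes from the noncentral t distribution with noncentrality d × √(n/2) and 2n − 2 degrees of freedom. At d = 0.8 the noncentrality is 0.8 × √16 = 3.20 with 32 per arm (62 df), and 0.8 × √13.5 = 2.94 with 27 per arm (52 df).

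| Patients remaining | Detectable difference at 80% power | Power at 0.8 SD |
|---|---|---|
| 64 (32 per arm) | 0.711 SD | 88.3% |
| 62.9 (31.45 per arm) | 0.718 SD | 87.7% |
| 54 (27 per arm) | 0.777 SD | 82.2% |

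Under the same assumptions, 80% power at 0.8 SD needs 25.5, so 26 per arm or 52 in all. Fifty-four still clears that.

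**Step 4: the same check with a different test.** The mention of 1 degree of freedom could point to a chi-square test. With noncentrality N × w², 80% power at 0.05 requires about 7.85. The detectable w is then √(7.85/64) = 0.35 with 64 patients and √(7.85/54) = 0.38 with 54. The change is again modest. The planned mixed model may differ from both approximations.

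**The case against.** The strongest reply is that no careful reader would be misled. Sections 3.1 and 11.1 are where the enrolment number and its derivation belong; both give 74, and 5.1 repeats it. They also show where 64 comes from, so the documents contain what is needed to see 3.3 as a slip. The outlier is one opening sentence in the eligibility criteria. On that reading nobody stops at 64, and the 54-patient case never arises. All of this stands, and it is why the point is minor. It does not remove the contradiction: 3.3 uses the language of recruitment and gives a different number.

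A reader might go further and infer that the trial is underpowered. The documents do not support that. The plan claims only to detect a large effect, and at an assumed 0.8 SD even 54 patients give about 82% power. Power of about 73% with 54 can be obtained, but only at 0.71 SD, a value the plan never names and which is back-solved to give 80% with 64 patients. The 54 is itself a worst case: 3.6 allows withdrawals to be replaced until enrolment closes, and a patient lost after week 6 can still contribute to the mixed model in 11.2.

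A reader might also infer that 74 is a miscalculation that needs its own correction. It differs from the division method by two patients, and the expected number remaining differs from 64 by about one. That is too little to carry a finding.

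**Conclusion.** The point holds as an internal contradiction of minor severity. Section 3.3 states a recruitment target of 64 against 74 in three other sections, most likely because the post-dropout figure was repeated there. That explanation is an inference, supported by the agreement of the three sections and by 64 × 1.15 rounding up to 74.

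The largest consequence, reached only if 3.3 is followed literally and no withdrawal is replaced, is a loss of 10 patients from the number behind the power statement and a rise of about 0.07 SD in the detectable difference. The contradiction itself and the patient counts rest on the documents alone. The SD and power figures rest on the assumed test, two-sidedness, equal arms after dropout and the 0.8 SD benchmark.

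**What to change.** In section 3.3, change *Sixty-four* to *Seventy-four*. Then 74 is the single recruitment target and 64 appears only as the number after dropout, as in 3.1 and 11.1.

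Optional, in the same edit: because 74 less 15% is 62.9, sections 3.1 and 11.1 could give the expected number after dropout as about 63, without specifying a per-arm split. The power claim is essentially unchanged.

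The cost is one word in one section, or a few words in three if the optional note is taken up. No patients or procedures are added beyond the 74 already planned. Under section 12.2 the change needs review board approval as a protocol amendment, so it can wait to be bundled with another amendment, provided staff are working to 74 in the meantime.

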3.4 Exclusion Criteria

Patients will be excluded if they are current heavy smokers (>10 cigarettes/day), have diabetes or other systemic diseases that may comprise healing, take antibiotics within 3 months before the procedure. Patients who stop smoking more than one year are eligible. Periodontal literature indicates risk factors for peri-implantitis (and reduced wound healing) as a history of periodontal disease, uncontrolled diabetes, and smokers (Schwarz et al. 2017).

3.5 Withdrawal Criteria

A subject may be discontinued from participation in the study for any of the following reasons:

1. Withdrawal of consent
2. Subject noncompliance with the protocol, as determined by the investigator
3. Any event or condition that would make continued participation in the study not in the best interest of the subject, as determined by the investigator
4. Pregnancy
5. Development of any medical condition that might affect the treatment and clinical outcomes, as determined by the investigator.
6. Initiation of any treatment or exposure that might affect the healing of therapy, as determined by the investigator.
7. Investigator discretion

3.6 Subject Replacement

Subjects who withdraw from the study can be replaced. However, to complete the study within the time allocated, the center will not enroll subjects after 24 months from enrollment initiation.

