4. TRIAL SCHEDULE

There will be three appointments including the baseline appointment and two follow-up appointments (6 weeks and 12 weeks) after therapy. The details of each visit will be mentioned in 6.3. Study Visits and Procedures.

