reviewed with all patients including techniques to clean around implants. Mechanical debridement of implant surfaces will be completed with titanium scalers and ultrasonics removing supragingival and subgingival plaque. Antimicrobial photodynamic therapy will be done at implant sites by applying a photosensitizing dye methylene blue (0.1 mg/ml) with a disposable syringe from the bottom of pocket in a coronal direction. The methylene blue dye will be diluted from 1.0% to 0.1% before use. The dye will be applied topically confined to the epithelialized space surrounding the implant fixture and will not be internalized. After 5 minutes in situ, the surrounding gingival tissues will be irradiated at six sites around the implant using a diode laser with a wavelength of 660nm, providing an energy density of 10 J/site, 100mW power, time equal to 100 seconds. After irradiation, the site will be thoroughly rinsed with saline. Only pockets \geq 4mm will be treated with the diode laser as this is the threshold pocket for diagnosing peri-implant inflammation per the 2017 World Work Workshop (Heitz-Mayfield & Salvi, 2018).

Clinical Measurements

Implant sites will be evaluated at baseline, six weeks, and twelve weeks after treatment (2 follow-up visits in total). Improvement in sites resulting from a reduction in inflammation will be analyzed based on pocket depth, clinical attachment loss, bleeding on probing, and the presence of plaque. For clinical measurements, six sites around the implant will be measured: mesial buccal, mid buccal, distal buccal, mesial lingual, mid lingual, and distal lingual. Bleeding on probing will be evaluated by gently sweeping the periodontal probe just within the gingival sulcus of the implant and the presence or absence of bleeding will be recorded. The presence or absence of plaque will then be evaluated at six sites around the implant surface. Plaque sampling will be performed prior to the remaining clinical measurements at the baseline/treatment appointment and 12 weeks after treatment utilizing a titanium curette within the gingival sulcus of the inflamed site. Periodontal pocket depth is measured from the free gingival margin to the base of the pocket, with a UNC periodontal probe with 1mm measurement units. Clinical attachment loss is measured by subtracting the pocket depth from distance of the free gingival margin to the implant platform.

Microbiologic collection and analysis

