The twelve weeks follow up will be the subjects last visit for this clinical trial. The patient will have clinical measurements taken as previously mentioned as well as possible radiographic measurements. If the patient has been diagnosed with peri-implant mucositis, recommendations will be made for continued maintenance of the diseased implant(s) and follow every 3 months. If the patient has been diagnosed with peri-implantitis, recommendations will be made for the possible need for surgical treatment.

d. Post Study Follow up and Procedures

[figure not shown]
The subjects will continue having routine maintenance appointments and/or treatments to follow up the outcomes related to the surgery and periodontal health in the periodontics clinic of UTSD. If the patients have symptoms or complications, the necessary treatments, will be performed.

e. Discontinuation Visit and Procedures

Subjects are free to withdraw from participation in the study at any time upon request. A subject may be discontinued from participation in the study for any of the following reasons:

1. Withdrawal of consent
2. Subject noncompliance with the protocol, as determined by the investigator
3. Any event or condition that would make continued participation in the study not in the best interest of the subject, as determined by the investigator
4. Pregnancy
5. Development of any medical condition that might affect the treatment and clinical outcomes, as determined by the investigator.
6. Initiation of any treatment or exposure that might affect the outcomes of implant therapy, as determined by the investigator.
7. Investigator discretion

Any subject with a serious adverse event, such as life-threatening diseases, hospitalization, that is ongoing at the time of discontinuation will be followed until the event returns to baseline, resolves, or stabilizes. If the serious adverse event does not meet these outcomes within 30 days after discontinuation or after study completion, the subject will be referred to an appropriate practitioner for continued care. If the study is discontinued, subjects will be referred back to the qualified clinicians for necessary dental care.

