8.3 Blinding

The investigator performing the treatment cannot be blinded because they will know if the dye has been applied and if the laser has been activated. Patient will be blinded because the control group will use a sham procedure including the use of saline and non-light emitting laser. The examiners will be blinded. The patients will be informed of benefits of all the procedures and realize that a minimum they are receiving the gold standard of peri-implant treatment, mechanical debridement.

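### Treated subjects can be discontinued with no further efficacy exams, and later replaced; if that loss is related to outcome and differs by arm, it could bias the comparison.

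*Combined protocol and SAP*

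**What the plan says.** **Withdrawal.** Section 3.5, headed as the withdrawal criteria, lists seven reasons for discontinuing a subject. Item 5 is a new medical condition that might affect treatment or outcome. Item 6 is "Initiation of any treatment or exposure that might affect the healing of therapy, as determined by the investigator". Item 7 is "Investigator discretion". Section 6.3e repeats the list, with item 6 worded as "Initiation of any treatment or exposure that might affect the outcomes of implant therapy, as determined by the investigator".

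**Replacement.** Section 3.6 states "Subjects who withdraw from the study can be replaced". Its only limit is that "the center will not enroll subjects after 24 months from enrollment initiation".

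**Timing.** Section 4 states: "There will be three appointments including the baseline appointment and two follow-up appointments (6 weeks and 12 weeks) after therapy". Section 6.3b places plaque sampling "at the baseline/treatment appointment and 12 weeks after treatment", so the baseline visit is also the treatment visit.

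**After discontinuation.** Sections 6.3e and 9.2 require follow-up of ongoing serious adverse events. They do not ask for efficacy measurements.

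**Knowledge of the arm.** Section 8.3 states: "The investigator performing the treatment cannot be blinded because they will know if the dye has been applied". The examiners are blinded. Sections 3.5 and 6.3e do not say which investigator decides on withdrawal.

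**Analysis.** Section 11.2c names a generalised linear mixed model over 0, 6 and 12 weeks. It defines no analysis set and gives no rule for the data of withdrawn or replaced subjects.

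**The concern.** In a trial with continuing treatment, discontinuing a subject at least stops exposure. Here the intervention is finished on the first day, so discontinuation during follow-up changes only whether the outcome is measured. Items 5 to 7 of section 3.5 rest on events and judgements that can arise after treatment and may be related to how the implant is doing. One possible route is a subject whose site stays inflamed, starts another therapy, meets item 6 and is not examined again.

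If this happens more often in one arm, the subjects left to be measured are no longer comparable. A real benefit could be hidden or a false one created. Blinded examiners protect the measurement, but not the decision about who stays to be measured.

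**Working it through.** **1. Is replacement needed to reach the target?** Sections 3.1 and 11.1 recruit 74, allow 15% dropout and want 64 (32 per arm).

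- 74 × (1 − 0.15) = 62.9, about one short of 64.
- 64 × 1.15 = 73.6, which rounds to the plan's 74.
- 64 / 0.85 = 75.3, so 76 would be needed to keep 64.

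The dropout allowance therefore covers the target to within about one patient without replacement.

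**2. Inputs for the illustration.** The 32 per arm and the 0.05 level come from the plan. The rest is assumed:

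- no true effect, and a normal outcome with SD 1;
- a two-sided two-sample t-test standing in for the planned mixed model;
- 5 of 32 subjects (15.6%, close to the plan's overall dropout rate) lost in one arm only;
- a correlation between the selection that drives removal and the outcome.

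The plan's 15% is an overall dropout rate. It is not a rate of outcome-driven removal in one arm.

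**3. Shift in the mean.** The expected sum of the 5 lowest of 32 standard normal values is −7.40.

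- Worst 5 removed, not replaced: the other 27 average 7.40 / 27 = 0.27 SD.
- Worst 5 removed, 5 unselected replacements with mean 0: 7.40 / 32 = 0.23 SD.
- With replacement at selection correlation 0.5: 0.5 × 0.231 = 0.12 SD. At 0.3: 0.3 × 0.231 = 0.07 SD. At 0: no shift.

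**4. Type I error** (40,000 simulated trials per case; Monte Carlo error about 0.2 percentage points or less):

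| Removal in one arm | Replaced? | Shift (SD) | Type I error |
|---|---|---|---|
| Exactly the worst 5 | no | 0.27 | about 21% |
| Exactly the worst 5 | yes, unselected | 0.23 | about 18% |
| Correlation 0.5 | yes, unselected | 0.12 | about 8% |
| Correlation 0.3 | yes, unselected | 0.07 | about 6% |
| Unrelated to outcome | yes, unselected | 0 | about 5% |

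The first two rows show where the bias comes from. It is present without replacement, and unselected replacements reduce it only by the factor 27/32. Losing the worst 5 in both arms and replacing them gave no mean shift, although type I error was 8.4% in 8,000 runs.

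**5. Scale.** With 32 per arm, 80% power in a two-sided t-test corresponds to a difference of 0.71 SD. The extreme shift with replacement is 0.23 / 0.71, about a third of that. At correlation 0.3 it is 0.07 / 0.71, about a tenth.

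**6. Can the mixed model recover the loss?** Only in part. If a subject leaves after week 6 and the data are kept, the model can use baseline and week 6, and it is valid if loss depends only on recorded values. It cannot recover a week 6 or week 12 value that was never collected when loss depends on deterioration that was not recorded.

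**The case against.** A reader might infer that the plan swaps out poor responders and so breaks the randomised comparison. The documents do not support that:

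- Poor response is not a listed reason for withdrawal, and the wording in 3.5 and 3.6 is permissive throughout. Item 6 also covers treatment that has nothing to do with the implant.
- Section 6.3c places advice on possible surgery at the week 12 visit, and 6.3d places treatment of symptoms or complications after the study. Some further care for poor responders is therefore described after the last outcome measurement.
- Section 3.6 speaks of subjects who withdraw, while 6.3e separates those free to withdraw from those who may be discontinued. Applying 3.6 to investigator-initiated removals is natural, because 3.5 is headed as withdrawal criteria, but it is an inference.
- Consent comes before a separately scheduled treatment visit (6.3a), so replacement may partly serve losses before treatment.
- Section 8.3 unblinds only the treating investigator. It is not established that whoever decides on withdrawal knows the arm.
- No passage says that a withdrawn subject's data are deleted.

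All of this stands, and it limits the point to what the rules allow. It does not remove it. Nothing confines discontinuation or replacement to the time before treatment, no efficacy exam is required afterwards, and no analysis rule offsets the loss.

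**Conclusion.** The point holds as a risk that the written rules leave open, not as a bias shown to occur. Two conditions must both be met for the estimated difference to be biased: removal is related to outcome, and it differs between arms. The source is discontinuation without further measurement. Blaming the replacement rule alone would be mistaken, since replacement merely fills a number that the dropout allowance already covers almost fully.

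Under the stated assumptions the shift lies between zero and 0.23 SD with replacement, with type I error between 5% and about 18%. Without replacement the extreme is 0.27 SD and about 21%. The upper figures need exactly the worst outcomes to be removed from one arm and none from the other, which is a worst case. Weaker selection (correlation 0.3 to 0.5) gives about 6% to 8%. None of these selection patterns comes from the documents. The change is worth making because it is cheap and because measurements not taken cannot be recovered later.

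**What to change.** - **Sections 3.5 and 6.3e:** state that a randomised and treated subject still attends the week 6 and week 12 exams unless consent is withdrawn. Record any further therapy or new condition, with its date, as an intercurrent event. This concerns measurement only and leaves the subject's care as it is.
- **Section 11.2c:** analyse all randomised subjects in their assigned arm, using all collected data.
- **Section 3.6:** limit replacement to subjects who leave before randomisation, or state that replaced subjects stay in the analysis. This change alone would not remove the bias; the first two do that work.

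**Cost:** wording in the protocol and analysis plan, plus follow-up exams for subjects who would otherwise have stopped attending. The downside is that some data collected after other therapy enter the main analysis and may dilute the effect slightly.
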